#### 3.2 RANDOMIZATION

Within each DeWorm3 study area, clusters will be randomly assigned in a 1:1 allocation ratio to either community-wide or standard of care MDA (Table 1). Restricted randomization will be performed to ensure balance of baseline factors by arm within each country, and stratified by region in India (Jawadhu Hills, n=8 vs. Thimiri, n=32).

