### 3.2.2 Cluster randomization

Clusters were randomized to community-wide versus targeted MDA stratified by country. Within each country, restricted randomization was performed to ensure balance between arms in baseline population and in factors hypothesized to be strongly associated with STH transmission intensity.

*The protocol for restricted randomization was as follows:*

Factors considered as part of the restricted randomization are age distribution, socio-economic status (SES), WASH access, urban / rural designation of clusters, and baseline STH prevalence as measured by Kato-Katz. Operationally, these factors and balancing criteria are defined as shown in Table 2.

Restricted randomization will be performed in Stata (StataCorp, College Station, Texas). Simulation of all possible 1:1 randomization scenarios will be performed and scenarios approved or rejected based on the balancing criteria. Validity will be checked and balancing criteria may be relaxed to ensure that the number of possible scenarios is not overly constrained, and that no two clusters are always or never assigned to the same arm; or conversely may be tightened to ensure a smaller number of possible scenarios.

**Table 2:** Factors chosen *a priori* to be balanced by restricted randomization

Balancing factor	Operational definition	Starting balancing criteria
Baseline STH prevalence	Prevalence of any STH by Kato-Katz, weighted by age.	1% absolute difference in mean prevalence
Age distribution	Proportion of the cluster population that are eligible for treatment in the standard of care arm (ages 1-19)	1% absolute difference in mean proportion eligible
Socio-economic status	Proportion of households with dirt floors (earth, dirt, dung)	1% absolute difference
WASH access	Proportion of households reporting no access to a toilet facility	1% absolute difference
Urban / rural designation	Cluster defined as urban or peri-urban by DeWorm3 Site Team	1 cluster difference
Total population	Total number of individuals in each arm	5,000 individuals
Cluster area	In km  .	2.0 km 

Once a list of approved scenarios has been prepared, DeWorm3 Site Data Teams will select the final randomization scenario by a random method of their choosing, such as a second Stata program or a public

lottery. The final scenario will be shared with the Central DeWorm3 Data Team along with a report of the randomization procedure.

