#### 3.3.1 Sample size calculations for Primary Objectives

**Objective 1.1** To compare the prevalence of the predominant STH species (*A. lumbricoides*, *A. duodenale*, *N. americanus* or *T. trichiura*) as measured by quantitative PCR 24 months after stopping MDA between clusters randomized to receive twice-yearly community-wide MDA versus clusters randomized to receive standard of care pre-SAC and SAC targeted MDA.

Power calculations for a range of scenarios were conducted. The following formula outlined by Hayes and Moulton [17]:

$$c = 1 + (Z_{\alpha/2} + Z_{\beta})^2 \frac{[\pi_0(1 - \pi_0) + \pi_1(1 - \pi_1)][1 + (m - 1)\rho]}{m(\pi_0 - \pi_1)^2}$$

was used to calculate the prevalence in the control clusters ( $\pi_0$ ) that would enable detection of a difference between arms with 80% power, given an endline prevalence in the intervention clusters ( $\pi_1$ ) of 2% and a range of assumptions of intraccluster correlation coefficient ( $\rho = 0.003$  to  $\rho = 0.005$ ), number of clusters per arm ( $c = 15$  to  $c = 20$ ) and number of people sampled per cluster ( $m = 500$  or  $m = 1,000$ ), assuming  $\alpha=0.05$ . The detectable alternative  $\pi_0$  ranged from 3% to 3.5%.

Power to detect differences in final prevalence between arms given plausible values for  $\pi_0$ , ranging from 7% to 10% (comparable to pre-intervention prevalences in each of the study sites), was then estimated using simulations conducted in R (R Center for Statistical Computing, Vienna, Austria). Each simulation assumed 1,000 individuals per cluster and a binomial distribution of STH prevalence with a mean of 2% in the intervention clusters and  $\pi_0$  in the targeted arm, a range of ICC and  $\alpha=0.05$ ; 10,000 repetitions were run for each scenario. Power was  $\geq 98\%$  for all scenarios simulated.

**Objective 1.2** To determine whether the transmission of the predominant STH species (*A. lumbricoides*, *A. duodenale*, *N. americanus* or *T. trichiura*) can be interrupted using MDA with albendazole.

Transmission interruption will be assessed at the cluster level and is defined as reaching a weighted point prevalence of  $\leq 2\%$  of that species as measured by quantitative PCR 24 months after stopping MDA. The proportion of clusters randomized to twice-yearly community-wide MDA versus standard of care pre-SAC and SAC-targeted MDA that interrupt transmission will be compared.

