#### Between-arm comparison of the proportion of clusters in which transmission has been interrupted

$$H_0: p_0 = p_1$$

$$H_A: p_0 \neq p_1$$

Simulations assumed 20 clusters per arm, 500 or 1,000 individuals per cluster ( $m$ ), and a binomial distribution of STH prevalence with a mean of 7% across clusters in the targeted arm ( $\pi_0$ ) and  $\pi_1$  in the intervention arm, a range of ICC ( $\rho = 0.003$  or  $\rho = 0.005$ ), and  $\alpha=0.05$ ; 10,000 repetitions were run for each scenario.

For a fixed mean endline prevalence of 7% in the targeted arm ( $\pi_0$ ), power to detect a difference in the proportion of clusters eliminated varies by number of individuals sampled per cluster, ICC and endline prevalence in the intervention arm ( $\pi_1$ ), as shown in Figure 1.

**Figure 1:** Power to detect a difference in the proportion of clusters achieving transmission interruption (Primary Objective 2.2.2) assuming 7% mean prevalence in the targeted clusters ( $\pi_0$ ), by mean endline prevalence in the intervention clusters ( $\pi_1$ ), intracluster correlation (ICC) and number of people measured per cluster ( $m$ ), estimated by simulation.

These power calculations demonstrate that with 20 clusters per arm, measuring STH infection among 1,000 people per cluster at endline would provide adequate power for the primary objectives in most scenarios.

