## SECTION 6: ANALYSIS

### 6.1 OUTCOME DEFINITIONS

The outcomes will be a) individual-level STH infection, defined as an individual's test result for the predominant STH (Objective 1.1) or any STH (Objective 2.1), and b) cluster-level transmission interruption, defined as a prevalence of the predominant STH species (Objective 1.2) or each STH species prevalent at baseline (Objective 2.2) of  $\leq 2\%$  with 95% confidence using a one-sided binomial test, as measured by qPCR 24 months after the final round of MDA.

We will classify each individual's infection status as negative (no amplification, Cycle threshold  $>40$ ), positive, or indeterminate; primary analyses will consider indeterminate results negative, while sensitivity analyses will recategorize indeterminate results as positive. Cycle thresholds indicating a positive or indeterminate result for each species will be defined and standardized by the DeWorm3 STH Molecular Support Unit.

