### 6.2 ANALYSIS METHODS

All analyses will be conducted separately for each site, unless otherwise specified.

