#### 6.2.1 Analysis of primary objectives

The effect of the primary exposure on endline infection with the predominant STH species at each site (Objective 1.1) will be analyzed using generalized estimating equations with Poisson family, with robust variance estimation and exchangeable correlation matrix. The primary exposure variable will be randomization arm, while the primary outcome will be individual-level STH infection status by qPCR (see Section 6.1).

Models will be adjusted for individual- and cluster-level covariates listed in Table 5. In the primary analyses, these data will be analyzed separately by site, while a secondary analysis will pool data across all sites and test for effect modification using an interaction term between study site and randomization arm.

**Table 5.** Individual- and cluster-level factors to be adjusted for in analysis of Objective 1.1.

Variable	Format	Data source
Cluster baseline age and gender-weighted STH prevalence	Continuous	LMC1 + CSS1
Population density within 0.5km of household	Continuous	Census 5
Household asset index quintile	Ordinal	Census 5
Water source Joint Monitoring Programme (JMP) classification	Ordinal	Census 5
Sanitation facilities JMP classification	Ordinal	Census 5
Hygiene facilities JMP classification	Ordinal	Census 5
Participant age	Continuous	Census 5
Participant gender	Categorical	Census 5
Household size	Continuous	Census 5
Migratory status	Binary	Census 5

The second primary objective of transmission interruption by cluster (Objective 1.2) will be defined as achieving an age- and gender-weighted cluster prevalence  $\leq 2\%$  of the predominant STH species by qPCR 24 months after the final round of MDA. The effect of the primary exposure on transmission interruption will be calculated by comparing the proportion of clusters in each arm in which transmission is successfully interrupted using a Fisher's exact test. In a sensitivity analysis, the proportion of clusters in which transmission is successfully interrupted will be compared using a weighted Chi test to account for sample size contributed by cluster in case not all clusters reach enrollment targets.

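### The India GEE models leave out the region within which India was randomised; separately, the robust variance has no small-sample correction at any site

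*SAP*

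**What the plan says.** SAP 3.2 describes restricted randomisation within each country and adds that it is "stratified by region in India (Jawadhu Hills, n=8 vs. Thimiri, n=32". SAP 3.2.2 gives the procedure but names only the country stratum: "Clusters were randomized to community-wide versus targeted MDA stratified by country".

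SAP 6.2 sets the unit of analysis: "All analyses will be conducted separately for each site, unless otherwise specified". The India result therefore rests on India's 40 clusters alone.

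For Objective 1.1, SAP 6.2.1 fits a GEE "with Poisson family, with robust variance estimation and exchangeable correlation matrix", adjusted for the ten covariates in Table 5. These are baseline cluster STH prevalence, local population density, asset quintile, water, sanitation and hygiene class, age, gender, household size and migratory status. Region is not among them. SAP 6.2.2 reuses the same model and covariates for Objective 2.1. No small-sample correction and no reference distribution are named.

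Objectives 1.2 and 2.2 compare the proportions of clusters interrupting transmission by an unstratified Fisher's exact test. Protocol section 7 leaves its covariate list open, but the SAP closes it with Table 5 and gives no reason for leaving region out.

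**The concern.** Stratifying by region forces the arms to be balanced on it. If the analysis then leaves region out, any prevalence difference between the regions stays in the residual variation between clusters, although it cannot contribute to the difference between arms. The standard error is then too large for the design that was run, and the test is conservative.

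Table 5's baseline prevalence term may stand in for region. How well it does so for Objective 1.1 is unknown: the term is STH prevalence without a named species, while the outcome is the predominant species. For Objective 2.1 the outcome is any STH, so the term matches better.

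A second question arises once region is considered. A robust variance from 40 clusters tends to be too small. Adding region removes the conservatism but leaves that problem, which Benin and Malawi share.

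**Working it through.** **1. The SAP's own figure.** SAP 3.3.1 uses c = 1 + (z₀.₀₂₅ + z₀.₂₀)² × [π₀(1−π₀) + π₁(1−π₁)] × [1 + (m−1)ρ] / [m(π₀−π₁)²], with π₁ = 2%. For m = 1,000, ρ = 0.005 and π₀ = 3.11%: 7.849 × 0.04973 × 5.995 / (1,000 × 0.0111²) ≈ 19.0, so c ≈ 20. Over c = 15 to 20, m = 500 or 1,000 and ρ = 0.003 to 0.005, the detectable π₀ runs from 2.89% to 3.44%. This agrees with the stated 3% to 3.5%. For control prevalences "ranging from 7% to 10% (comparable to pre-intervention prevalences in each of the study sites", power is about 100%, in line with the stated 98% or more.

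**2. What a regional gap adds.** The documents give no regional prevalences, so gaps are assumed. Take an overall mean of 2.5% and a two-fold gap, with the 8-cluster region higher (4.17% vs 2.08%). The between-region share of the ICC is 0.2 × 0.8 × (0.0417 − 0.0208)² / (0.025 × 0.975) = 0.0028, more than half of 0.005. If the 32-cluster region were the higher one (2.78% vs 1.39%), the share would be 0.0013 and the effects below would be smaller.

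**3. Simulation of Objective 1.1 in India.**
- Design: 40 clusters of 1,000, allocated 4:4 and 16:16 within region, with Table 2's 1-point restriction on baseline prevalence.
- Baseline: 650 people per cluster (protocol 4.4), assumed mean 8.5%, assumed within-region baseline–endline correlation 0.5.
- Total ICC 0.005 including region. The three-fold null runs and the 2% vs 7% runs use 0.005 within region.
- Model: log-linear Poisson with arm, baseline prevalence, and with or without region. Its robust z matched an individual-level exchangeable Poisson GEE (−3.232 for both).
- Runs: 6,000 per power scenario (2,000 at 2% vs 7%) and 20,000 per null scenario.
- SAP as written is read as the uncorrected robust variance with a normal reference. KC is the Kauermann-Carroll variance with a t reference.

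A gap is called carried if baseline prevalence shows the same regional ratio, and not carried if it shows none.

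Type I error, nominal 5%:

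| Scenario | SAP as written |
|---|---|
| Regions alike, or gap carried | 6.5–7.3% |
| Two-fold gap, not carried | 1.1% |
| Three-fold gap, not carried | 0.2% |

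With region added and no correction, the error is 7.5–8.4%. With region and KC it is 5.0–5.6%; with region and the Mancl-DeRouen variance and t it is 3.6–4.3%. Bias in the log rate ratio was at most 0.004 in a separate set of runs.

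Power at 2% vs 3%:

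| Scenario | SAP as written | KC, no region | KC, with region |
|---|---|---|---|
| Regions alike | 82.6% | 78.5% | 78.5% |
| Two-fold, carried | 96.7% | 95% | 96% |
| Two-fold, not carried | 86.0% | 81% | 96% |

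With the same corrected variance, power without and with region is 99% vs 100% at 2% vs 3.5%, and 100% either way at 2% vs 7%, even with a three-fold gap.

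**4. Sensitivity.** Varying the baseline mean (3% to 8.5%) and the correlation (0 to 0.9), the KC gain from region is 8 to 16 points when the gap is not carried. When it is carried, the gain is 0 to 5 points, or up to 11 if baseline otherwise does not predict endline. If one other Table 5 covariate correlates 0.5, 0.7 or 0.9 with region, the 16-point gain falls to 12, 8 or 2 points.

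**5. The variance problem without region.** With regions alike and region out of the model, type I error is about 7%. With eight further cluster-level covariates it is about 12%. No regional feature enters these runs, so they apply equally to Benin and Malawi, which have 40 clusters each.

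**6. Fisher's test.** SAP 6.1 requires the 2% threshold to be met "with 95% confidence using a one-sided binomial test". With 1,000 people the cut-off is 12 positives, because at 2% P(X ≤ 12) = 0.038 and P(X ≤ 13) = 0.064. With the control arm at the SAP's "mean of 7% across clusters in the targeted arm" and the intervention arm at 2%, power of the pooled Fisher test vs a region-stratified exact test is:

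| ICC | Regions alike | Two-fold gap | Three-fold gap |
|---|---|---|---|
| 0.005 | 66% vs 56% | 83% vs 82% | 96% vs 96% |
| 0.003 | 39% vs 30% | 69% vs 68% | 93% vs 93% |

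If the rule is simply an observed prevalence of 2% or less, both tests have 99.8–100% power.

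**The case against.** The strongest reply is that this changes little. At the planning effect power is complete with or without region. The 15-point difference needs three things together: a true effect at the bottom of the detectable range, a sizeable regional gap, and Table 5 covariates that miss it. Baseline prevalence, density, assets and the water, sanitation and hygiene classes may well absorb most of a regional difference; only one such proxy was simulated. This stands, and it sets the priority.

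It can also be said that the liberal variance has nothing to do with region. That stands too: it comes from the number of clusters, so a correction confined to India would leave two sites exposed.

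On the other side, a reader might infer that the India estimate is biased. It is not, because the arms are balanced on region by design. A reader might infer that the India test is always conservative. It is so only when region matters beyond Table 5; otherwise it is liberal. A reader might take "Clusters were randomized to community-wide versus targeted MDA stratified by country" as contradicting SAP 3.2. It does not, since a region stratum can sit inside a country stratum; 3.2.2 merely does not repeat it. And a reader might conclude that Fisher's test should be stratified, but at the planning values that gains nothing and can cost up to 10 points.

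**Conclusion.** The omission is real for the India GEE models of Objectives 1.1 and 2.1. It affects calibration and efficiency, not bias. Under an assumed two-fold gap not carried by baseline, type I error is about 1% and power at 2% vs 3% is about 81% instead of 96%. With regions alike, including region costs nothing measurable. Priority is low to moderate: one site of three, no effect at 2% vs 7%, and no regional data in the documents.

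The uncorrected robust variance is a separate issue at all sites: about 7% type I error in the model run here. The 12% figure is a stress case, since most of Table 5 is measured at household or individual level and would matter this much only if it varied mainly between clusters.

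The figures rest on assumed regional gaps (the 8-cluster region higher), equal cluster sizes, an assumed baseline–endline correlation, and reading the SAP as an uncorrected variance with a normal reference. Objective 2.1 was not simulated separately. The other Table 2 restrictions and the individual-level covariates were not simulated.

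**What to change.** 1. Add region (Jawadhu Hills or Thimiri) to Table 5 for the India models of Objectives 1.1 and 2.1. In the pooled secondary model, add an India region indicator and keep the three-level site-by-arm interaction test as it is.
2. At all three sites, specify a small-sample-corrected robust variance (for example Kauermann-Carroll, closest to 5% in these runs) with a t reference. Define the degrees of freedom as 40 clusters less the number of cluster-level parameters actually fitted. The four-parameter model above gives 36, but the SAP should state the rule and the count for each site, not fix that number.
3. Keep Fisher's exact test as primary for Objectives 1.2 and 2.2.
4. Repeating the region stratum in SAP 3.2.2 would be an editorial courtesy.

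The cost is SAP wording, since region is known for every India cluster. Intervals widen slightly, and nominal power falls where the uncorrected test was liberal: 82.6% to 78.5% at 2% vs 3% with regions alike, because type I error falls from 7.2% to 5.5%. Making the change before endline results are seen avoids a post hoc choice of model.

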**Table 1: Standard of care MDA strategy and eligibility for MDA by arm in each of the DeWorm3 study sites**

Study site	Standard of care MDA strategy	Intervention arm community-wide MDA
Benin	Annual School-based MDA Targets pre-school age and school age children ( 1-14 years old )	Twice-annual community-wide household MDA Individuals aged ≥1 year Not currently in the first trimester of pregnancy or acutely ill
India	Twice-annual National Deworming Days utilizing school- and community-based distribution Targets pre-school age and school age children ( 1-19 years old )	Twice-annual community-wide household MDA Individuals aged ≥1 year Not currently in the first trimester of pregnancy or acutely ill
Malawi	Annual School-based MDA and Child Health Days Targets pre-school age and school age children ( 2-19 years old )	Twice-annual community-wide household MDA Individuals aged ≥2 years Not currently in the first trimester of pregnancy or acutely ill

##### 3.2.1 Cluster demarcation

Clusters were defined by each DeWorm3 Site Team, in collaboration with the Central DeWorm3 Data Team. All clusters must be contiguous and have a minimum population of 1650 individuals. Whenever possible, clusters correspond to existing administrative units.

*The protocol for cluster identification consisted of the following steps:*

- Review a list of the communities (villages / neighborhoods / settlements) identified in the DeWorm3 baseline census and the total population of each according to household affiliation.
  - If an individual community has a population within the range identified for Cluster size, that community should be considered an independent cluster and boundaries drawn based on the location of each participating household.
  - Where communities are too small to compose an independent cluster, GPS coordinates, field reports and the ArcMap / Google Earth map of the study area should be used to identify

- communities and/or non-community-affiliated households that can reasonably be combined to form a cluster with a population within the proposed range.
- iii. Where communities are too large to be considered a single cluster, GPS coordinates, field reports and an ArcMap / Google Earth map of the study area should be used to identify intuitive boundaries that result in clusters with populations within the proposed range.
  - b. Households not listed as belonging to a specific community should be assigned to a cluster based on geographic features and/or distance from the center of the nearest clusters to the household's GPS coordinates.
    - i. Where a household is equidistant between the center of two clusters, geographic features and/or the location of schools attended by children in the household may be used to make a determination.
  - c. Once the DeWorm3 baseline census database has been coded to reflect the cluster boundaries, this database will be sent back to the Central DeWorm3 Data Team who will review the GPS coordinates of households in each cluster to verify that households affiliated with each community fall within cluster boundaries identified. Cluster boundaries will also be reviewed in relation to geographical boundaries such as rivers and transport boundaries such as main roads.
  - d. Where necessary, households may be reassigned by the Central DeWorm3 Data Team to a different cluster based on cluster boundaries and GPS coordinates.

### 3.2.2 Cluster randomization

Clusters were randomized to community-wide versus targeted MDA stratified by country. Within each country, restricted randomization was performed to ensure balance between arms in baseline population and in factors hypothesized to be strongly associated with STH transmission intensity.

*The protocol for restricted randomization was as follows:*

Factors considered as part of the restricted randomization are age distribution, socio-economic status (SES), WASH access, urban / rural designation of clusters, and baseline STH prevalence as measured by Kato-Katz. Operationally, these factors and balancing criteria are defined as shown in Table 2.

Restricted randomization will be performed in Stata (StataCorp, College Station, Texas). Simulation of all possible 1:1 randomization scenarios will be performed and scenarios approved or rejected based on the balancing criteria. Validity will be checked and balancing criteria may be relaxed to ensure that the number of possible scenarios is not overly constrained, and that no two clusters are always or never assigned to the same arm; or conversely may be tightened to ensure a smaller number of possible scenarios.

**Table 2:** Factors chosen *a priori* to be balanced by restricted randomization

Balancing factor	Operational definition	Starting balancing criteria
Baseline STH prevalence	Prevalence of any STH by Kato-Katz, weighted by age.	1% absolute difference in mean prevalence
Age distribution	Proportion of the cluster population that are eligible for treatment in the standard of care arm (ages 1-19)	1% absolute difference in mean proportion eligible
Socio-economic status	Proportion of households with dirt floors (earth, dirt, dung)	1% absolute difference
WASH access	Proportion of households reporting no access to a toilet facility	1% absolute difference
Urban / rural designation	Cluster defined as urban or peri-urban by DeWorm3 Site Team	1 cluster difference
Total population	Total number of individuals in each arm	5,000 individuals
Cluster area	In km  .	2.0 km 

Once a list of approved scenarios has been prepared, DeWorm3 Site Data Teams will select the final randomization scenario by a random method of their choosing, such as a second Stata program or a public

lottery. The final scenario will be shared with the Central DeWorm3 Data Team along with a report of the randomization procedure.

